	Class II	Diffuse astrocytoma, mixed oligoastrocytomas, oligodendrogloma, pleomorphic xanthoastrocytoma, hairy myxoid astrocytoma
	Class III	Anaplastic astrocytoma, anaplastic oligodendrogloma, anaplastic oligoastrocytomas
	Class IV	Primary and secondary glioblastoma

Isocitrate dehydrogenase (IDH), located in the long arm of chromosome 2 (2q33), is a key rate-limiting enzyme in the tricarboxylic acid cycle, providing energy for cell metabolism and precursors of biosynthesis. There are three isomerases in the IDH gene family (IDH1, IDH2 and IDH3). IDH1 or IDH2 mutations lead to the accumulation of 2-hydroxyglutaric acid, another new metabolite, in cells, which can not only lead to abnormal histone modification, but also increase the activity of VEGF pathway, thereby inducing tumorigenesis. The data showed that IDH1/2 gene mutation was an early genetic mutation in the development of glioma. It usually occurs in young adults and

adolescents with diffuse glioma. IDH1/2 mutation had a certain distribution pattern corresponding to WHO classification, which was mainly distributed in grade II~III oligodendrogloma (69.2%), astrocytoma (79.8%), oligoastrocytomas (75.5%) and grade IV secondary glioblastoma (73%), but rare in primary glioblastoma (<5%) and childhood glioblastoma.

IDH1 mutations accounted for more than 90% of IDH1 and IDH2 gene mutations, among which IDH1 R132H (CGT>CAT, arginine replaced by histidine) mutations were the most common, accounting for about 90% of IDH1 mutations.

The National Comprehensive Cancer Network (NCCN) Clinical Practice Guidelines for Central Nervous System Cancer (V1, 2015) include the presence or absence of IDH1 or IDH2 gene mutations as one of the indicators to assess the risk type of patients with low-class glioma. The Chinese Guidelines for molecular Diagnosis and Treatment of glioma (2014) also included IDH1 or IDH2 gene mutation as the preferred molecular marker for molecular pathological typing (grade I evidence).

At present, the gold standard method for clinical detection of IDH gene mutation is nucleic acid sequencing. However, this method is time-consuming and laborious to determine the detection results, and the operation process is complex, so it is difficult to widely apply this technique in clinical practice.

2 Research Purpose

By using this product to detect the IDH1 R132H gene mutation in the cancer cells of patients with glioma, compare it with the results of nucleic acid sequence determination, and combine the results of clinicopathological typing to confirm and evaluate the safety and effectiveness of this product.

3 Trial Design

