3.1 Overall Design of the Trial

This study followed the principle of synchronous blind method. Enrolled cases were coded and compared with the nucleic acid sequence determination of the control method (gold standard). Results were determined independently according to the critical value or interpretation requirements provided by each method, and relevant statistics were conducted. Combined with the results of clinicopathological classification, the incidence of IDH1 gene R132H mutation in different subtypes was counted to evaluate the clinical application performance of this product

The total number of samples for clinical research should be no less than 1,000 cases, and clinical trials should be carried out in no less than 3 (including 3) provincial health care institutions or specialized hospitals to ensure that the results are statistically significant. All samples should have corresponding basic clinical information, including: patient visiting No. / medical record number/specimen number, age, sex, pathological diagnosis result, etc.

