4.3 Evaluate the conformity between the kit and the reference method

- (1) If the results to be tested and the reference results are both positive or negative, it is regarded as in conformity.
- (2) In the event that the result to be tested is positive and the reference result is negative, or the result to be tested is negative and the reference result is positive, it is recorded as non-conformity.
- (3) If the result to be tested fails and the reference method has confirmed results, it shall be recorded as non-conformity. The reasons and results of the non-conformity shall be truthfully recorded, and the comparison results shall be repeatedly confirmed when necessary.
- (4) Complete subsequent statistical analysis based on the above statistical results.

5 Statistical methods

Statistical analysis of clinical study data: Kappa test was used for statistical analysis of the comparison between the kit test results and gene sequencing test results, and then the difference between the results obtained by the two methods was compared. If $\text{Kappa} > 0.6$, it was proved that there was no statistical difference between the two methods in detecting IDH1 gene mutations in glioma samples.

6 Duration of clinical trials and its reasons

The clinical study lasted about 6-8 months from the drafting of the protocol, project approval, ethical review, agreement signing, specimen collection, the beginning of the test to the end of the trial, and the report and seal are completed. If the sample collection is smooth and the number of samples meets the test requirements, the clinical trial time can be shortened; if it is not smooth, the time can be appropriately extended.

7 Inclusion criteria, exclusion criteria and rejection Criteria

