7.3 Rejection Criteria

- (1) Samples considered by the researcher to be unsuitable for continuing clinical trials, such as samples that have not been prepared in accordance with the required steps.
- (2) Samples with unqualified genomic DNA quality, such as:
 - ① DNA concentration is less than 10ng/μL;
 - ② Genomic DNA was severely degraded or had insufficient purity, and OD260/OD280 exceeded the range of 1.6~2.0.
- (3) Samples whose repeated test results of reference methods failed.
- (4) Samples with incomplete clinical basic information (patients' visiting No. / medical record No./specimen No., age, sex, pathological diagnosis result).

8 Provisions for amendments to clinical trial protocols

Any modification to the protocol during the test should be explained, and the time, reason, process and record of the modification should be elaborated in detail, and its impact on the evaluation of the whole study results should be demonstrated.

9 Ethical issues and explanations of clinical trials

This clinical trial verification test uses the patient's pathological specimens in the previous treatment process. It is limited to in vitro diagnosis, does not directly contact the patient, does not cause any harm to the patient, and only compares the performance of the reagent with the control reagent. The results are only used for study and analysis related to this test, and will not guide the diagnosis and treatment of patients based on this, so it will not have any adverse effects on the human body.

This clinical trial strictly complies with the "Declaration of Helsinki", and this clinical verification trial involves relevant patient data. Such as: Patient visiting No. / medical record No. / specimen No., age, sex, pathological diagnosis result, etc. The hospital and Genetron Health (Beijing) Co., Ltd. will jointly undertake the confidentiality of the patient information, and the clinical trial operator and clinical validation unit promise not to disclose the content related to the subject specimen.

Therefore, the clinical trial was verified to submit an informed consent exemption to the ETHICS Committee.

10 Data processing and record keeping

It is required to keep all experimental records during the clinical trial, the results should be objective, timely and serious, and the operator and operation time should be recorded. Medical institutions shall keep the clinical trial data for five years after the termination of the trial.

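### Section 2 sets out to confirm the kit's safety, but the planned analysis has no safety measure, and kappa > 0.6 does not limit wrong or failed results

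*Combined protocol and SAP*

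**What the plan says.** Section 2 gives the purpose in one sentence. The kit is used to detect IDH1 R132H, the investigators "compare it with the results of nucleic acid sequence determination", and, with the clinicopathological typing added, they are to "confirm and evaluate the safety and effectiveness of this product". The supplied text does not mention safety again.

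The planned outputs are these:

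- Section 3.1: "the incidence of IDH1 gene R132H mutation in different subtypes was counted to evaluate the clinical application performance of this product". This is a descriptive count and is tied to performance.
- Section 4.3: each sample is classed as conforming or not. A kit positive with a negative reference is a non-conformity, "or the result to be tested is negative and the reference result is positive, it is recorded as non-conformity", and a kit failure is also a non-conformity when the reference gives a result. Reasons for non-conformity are to be recorded.
- Section 5: "Kappa test was used for statistical analysis of the comparison between the kit test results and gene sequencing test results". If kappa exceeds 0.6, "it was proved that there was no statistical difference between the two methods in detecting IDH1 gene mutations in glioma samples".

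Section 9, in support of a consent exemption, says the study uses specimens from earlier treatment and is limited to in vitro testing, that it "does not directly contact the patient, does not cause any harm to the patient", and that results will not guide care. Section 7.2 adds that the selection of subjects has no adverse effect on their health.

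**The concern.** An objective that a trial sets out to confirm needs a measure and a rule for judging it. Safety has neither here. Section 9 explains why the study itself exposes nobody to harm. That is a statement about the conduct of the study and does not evaluate the product.

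For a test run only on tissue, the product harm these data could bear on is a wrong or missing answer when the kit is later used. The background section says why that would matter: it describes IDH mutation status as an input to risk assessment in low-grade glioma and as a preferred marker for molecular typing. A missed mutation, a false mutation call and a failed test are different errors, and a reader judging safety needs each one separately. The plan merges them, so a kit could meet the trial's only criterion while its rate of missed mutations was high and never reported as such.

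**Working it through.** **1. Text check.** The aim in Section 2 was set beside every planned output.

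| Place | What is planned | Safety measure? | Safety criterion? |
|---|---|---|---|
| Section 3.1 | R132H incidence by subtype | No | No |
| Section 4.3 | Conforming / non-conforming, including kit failures | Relevant results recorded, not defined as safety | No |
| Section 5 | Kappa, threshold 0.6 | No | No |
| Sections 7.2 and 9 | Argument that subjects are not at risk | Nothing measured | No |

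The plan gives no safety figure to reproduce.

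**2. Does kappa > 0.6 limit the error rates?** Inputs from the plan are the minimum of 1,000 samples (Section 3.1) and the threshold of 0.6 (Section 5). The documents do not give the case mix, so the number of sequencing-positive samples, P, is an assumption and is varied below. No failed tests are assumed.

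Let n = 1,000, FN = missed mutations, FP = false calls, and K = P − FN + FP = kit positives.

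- Observed agreement: po = 1 − (FN + FP)/n
- Chance agreement: pe = [P·K + (n − P)(n − K)]/n²
- Kappa = (po − pe)/(1 − pe)

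Take P = 300, FN = 144, FP = 0, so K = 156:

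- po = 1 − 144/1,000 = 0.856
- pe = 0.300 × 0.156 + 0.700 × 0.844 = 0.0468 + 0.5908 = 0.6376
- kappa = (0.856 − 0.6376)/(1 − 0.6376) = 0.2184/0.3624 = 0.603

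With one more miss (FN = 145), po = 0.855, pe = 0.6380 and kappa = 0.2170/0.3620 = 0.599. So 144 is the largest number of misses that still passes. The same search at other assumed values of P, with FP = 0, gives:

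| Sequencing-positive (assumed) | Most misses that pass | Share missed | Kappa |
|---|---|---|---|
| 300 | 144 | 48% | 0.603 |
| 400 | 177 | 44% | 0.602 |
| 600 | 208 | 35% | 0.601 |

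**3. Does kappa show which error occurred?** Keep P = 300 and reverse the error: FN = 0, FP = 199, K = 499.

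- po = 0.801
- pe = 0.300 × 0.499 + 0.700 × 0.501 = 0.1497 + 0.3507 = 0.5004
- kappa = 0.3006/0.4996 = 0.602

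A kit that misses 48% of mutations and makes no false calls, and a kit that misses none and calls 199/700 = 28% of negatives positive, have almost the same kappa (0.603 and 0.602). The statistic does not tell them apart.

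**4. What direct reporting would show.** For zero events in m samples, the exact two-sided 95% upper limit is 1 − 0.025^(1/m). With no misses among an assumed 300 positives this is 1 − 0.025^(1/300) = 1.2%; among an assumed 40 it is 1 − 0.025^(1/40) = 8.8%. For the kit in step 2, the exact (Clopper–Pearson) interval for 144/300 is 42.2% to 53.8%. Either result would tell the reader plainly what kappa alone does not.

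**The case against.** The strongest reply has four parts.

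- **Section 2 is one paired aim with one stated means**, comparison with sequencing together with typing. A reader might infer that half of the purpose cannot be answered. The documents do not support that: they set no separate safety objective, and Section 4.3 records false positives, false negatives and failures. What is missing is the definition, the separate tabulation and the criterion.
- **Direct risk to subjects is dealt with by argument** in Sections 7.2 and 9. This stands for the study's conduct. It does not evaluate the product.
- **No passage says that a passing kappa will be reported as showing safety.** This is correct. Section 5 ties kappa only to the lack of a difference between the methods. A reader might infer such a report from Sections 2 and 5 together, but it is a possibility that the wording leaves open and not something planned.
- **Defining safety as error and failure risk is a reviewer's choice**, and the lack of direction-specific agreement is a weakness of Section 5 whatever Section 2 says. Both statements are fair. The protocol offers no other definition, however, and this is the only one its data can serve. If the sponsor does not accept it, the word should leave Section 2.

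The miss counts in the working are extreme cases chosen to show what the criterion allows. They do not predict how the kit will perform.

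**Conclusion.** The point holds as a mismatch between a stated aim and the planned analysis. Section 2 promises confirmation of safety; Section 5 contains no safety measure or criterion; Section 9 speaks only to the risk to study subjects. The data that could address the remaining question, wrong or failed results, will be recorded but are pooled and summarised only through kappa.

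The gap is material because the kappa rule gives little protection on that question: under the assumptions in the working, between 35% and 48% of mutations could be missed with kappa still above 0.6. Those figures rest on the 1,000-sample minimum, assumed positive counts of 300 to 600, no false positives and no failures. The text finding needs none of these assumptions. It covers the supplied text only; the study route in Section 3.3 is not shown.

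Nothing here changes the calculation of kappa or the sample size, and the point does not claim that the agreement analysis is invalid.

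**What to change.** Either of two changes resolves the point. The first is preferable because it adds information.

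1. **Define and report.** State in Section 2 that safety means the risk of a wrong or failed kit result. Add to Section 5, each with an exact 95% confidence interval:
   - false-negative proportion: kit negative among sequencing-positive samples with a kit result;
   - false-positive proportion: kit positive among sequencing-negative samples with a kit result;
   - failed-test proportion: kit failures among all samples with a sequencing result.

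   State that samples removed under Section 7.3 are outside these denominators, and give their number. Draw no other safety conclusion.
2. **Remove.** Take safety out of the purpose in Section 2 and refer to Section 9 for the risk to subjects.

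The first option costs one short table from results that Section 4.3 already records, with no new samples or tests and no change to the kappa criterion. Its drawback is a narrower safety claim. The second costs one wording change, but leaves the error rates unreported unless they are added to Section 5 in any case.

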3.1 Overall Design of the Trial

This study followed the principle of synchronous blind method. Enrolled cases were coded and compared with the nucleic acid sequence determination of the control method (gold standard). Results were determined independently according to the critical value or interpretation requirements provided by each method, and relevant statistics were conducted. Combined with the results of clinicopathological classification, the incidence of IDH1 gene R132H mutation in different subtypes was counted to evaluate the clinical application performance of this product

The total number of samples for clinical research should be no less than 1,000 cases, and clinical trials should be carried out in no less than 3 (including 3) provincial health care institutions or specialized hospitals to ensure that the results are statistically significant. All samples should have corresponding basic clinical information, including: patient visiting No. / medical record number/specimen number, age, sex, pathological diagnosis result, etc.

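### R132H frequency by subtype is used to judge the kit, but it is not an accuracy measure; report kit-versus-Sanger agreement by subtype instead

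*Combined protocol and SAP*

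**What the plan says.** Section 2 (Research Purpose) compares the kit with sequencing and adds that the study will "combine the results of clinicopathological typing to confirm and evaluate the safety and effectiveness of this product". Section 3.1 gives the typing part its content: "the incidence of IDH1 gene R132H mutation in different subtypes was counted to evaluate the clinical application performance of this product". It does not say whether kit or Sanger results are counted. It gives no expected frequency and no acceptance limit.

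Accuracy is addressed by the paired comparison. Section 3.1 pairs each coded case with Sanger sequencing, and section 4.3 classes each pair as conforming or not. Section 5 names one method: "Kappa test was used for statistical analysis of the comparison between the kit test results and gene sequencing test results". Success is kappa above 0.6. No section plans agreement within a subtype.

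Sections 3.2.2 and 7.1 require a pathological diagnosis for every sample. Section 3.2.2(2) admits glioma, other brain tumours and normal tissue. The proportions are not given.

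**The concern.** The plan gives the subtype count an evaluative role, but a frequency cannot fill it. A Sanger frequency describes the patients and not the kit. A kit frequency mixes true and false positives, so a plausible value does not show that the right samples were called positive.

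What could be missed is a weakness confined to one tumour type. A subtype that contributes few positives has little weight in a pooled kappa, and a shortfall in its frequency can look like ordinary rarity. Primary glioblastoma is the obvious case, because the background text puts IDH1/2 mutation there below 5%. The trial could then report good pooled agreement and plausible subtype frequencies for a kit that does not work in that tumour.

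**Working it through.** **Plan's own figure.** The only size given is at least 1,000 samples (section 3.1). It cannot be reproduced, because no error rate, power, expected agreement or subtype mix is stated. The point does not depend on it.

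**1. Failure confined to one subtype.** The mix is assumed, since the documents give none. The kit is perfect except that it misses every mutation in primary glioblastoma.

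| Group | Samples | Sanger positive | Kit positive | Agree |
|---|---|---|---|---|
| Other gliomas, 60% positive | 500 | 300 | 300 | 500 |
| Primary glioblastoma, 4% positive | 300 | 12 | 0 | 288 |
| Negative tissue | 200 | 0 | 0 | 200 |
| Total | 1,000 | 312 | 300 | 988 |

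- Observed agreement: 988/1,000 = 0.988.
- Chance agreement: 0.312 × 0.300 + 0.688 × 0.700 = 0.0936 + 0.4816 = 0.5752.
- Kappa: (0.988 − 0.5752)/(1 − 0.5752) = 0.4128/0.4248 = 0.97.
- Pooled positive agreement: 300/312 = 96.2%, so a pooled figure does not expose the failure either.
- Kit frequency in glioblastoma: 0/300 = 0%, consistent with under 5%.
- Positive agreement in glioblastoma: 0/12. The Wilson 95% upper limit is 1.96²/(12 + 1.96²) = 3.84/15.84 = 24%.

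**2. A less favourable mix.** Assume 800 primary glioblastomas with 32 positives, 100 other gliomas with 60 positives and 100 negatives, and the same kit. Agreement is 968/1,000. Chance agreement is 0.092 × 0.060 + 0.908 × 0.940 = 0.8590. Kappa is (0.968 − 0.8590)/0.1410 = 0.77, still above 0.6.

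**3. Offsetting errors.** For true frequency p, sensitivity Se and specificity Sp, the kit's apparent frequency is q = p·Se + (1 − p)(1 − Sp).

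- p = 0.50, Se = Sp = 0.80: q = 0.40 + 0.10 = 0.50, the true value.
- p = 0.05, Se = 0.80: q stays at 0.05 if 1 − Sp = 0.05 × 0.20/0.95 = 0.011.
- In the mix of step 1, add 12 false positives in glioblastoma to the 12 misses. Kit and Sanger both show 12/300. Agreement is 976/1,000 and chance agreement is 0.312² + 0.688² = 0.5707. Kappa is (0.976 − 0.5707)/0.4293 = 0.94, with positive agreement in glioblastoma still 0/12.

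**4. Moderate error in one direction.** The background text gives 79.8% IDH1/2 mutation in grade II–III astrocytoma, and says that "IDH1 mutations accounted for more than 90% of IDH1 and IDH2 gene mutations" and that R132H is the commonest of these, "accounting for about 90% of IDH1 mutations". Taking 0.90 for each share, and assuming both apply in astrocytoma, p = 0.798 × 0.81 = 0.646. With Se = 0.90 and Sp = 1, q = 0.582. A two-sided 5% test against an exactly known 0.646 would have power of about 28% with 100 samples and 48% with 200. The plan has no such test and no known frequency.

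**The case against.** Several points on the other side stand.

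- **One kit cannot hide everywhere.** With Se = Sp = 0.80, primary glioblastoma at p = 0.05 would show 0.05 × 0.8 + 0.95 × 0.2 = 23% positive, which is conspicuous. The kit with Se 0.80 and Sp 0.989 would show 40.6% where the truth is 50%. A reader might infer that the count cannot detect a bad kit. That is too strong: gross errors common to all types would distort the pattern.
- **The kappa rule gives protection.** With Se = Sp = 0.80, agreement is 0.80 and kappa is at most (0.80 − 0.50)/0.50 = 0.60, which does not exceed the limit.
- **The count decides nothing.** A reader might take it as a separate proof of effectiveness. Section 2 only combines typing with the sequencing comparison, and the sole success rule is kappa.
- **Counting by both methods is a fair reading of section 3.1.** In step 1 that would show 0% by kit against 4% by Sanger. The plan does not say so, however, and the last case in step 3 shows that equal frequencies can still hide errors.

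Two further inferences lack support. The background percentages are IDH1/2 rates, but no section makes them a target, so a mismatched benchmark cannot be charged to the plan. The background text says a guideline "included IDH1 or IDH2 gene mutation as the preferred molecular marker for molecular pathological typing", but section 3.1 uses clinicopathological classification, and the visible Table 1 entries are histological names. Nothing shows that IDH status entered the subtype labels, so circularity is not established.

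It can also be argued that subtype agreement is too imprecise to help: 4 of 4 has a Wilson lower limit of 4/(4 + 3.84) = 51%. That limits how firmly good performance can be confirmed. It does not stop 0 of 4 or 0 of 12 from being seen.

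**Conclusion.** The point holds in a limited form. The subtype count is a descriptive frequency to which section 3.1 assigns an evaluative purpose. It has no stated source, no sample-level comparison and no criterion, so it adds no direct evidence of accuracy. It can miss moderate errors, offsetting errors and errors confined to one subtype. The pooled kappa does not close the last gap: kappa is about 0.97 in one assumed mix and 0.77 in a more extreme one, with no glioblastoma mutation detected in either.

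These sizes rest on assumed subtype mixes, an assumed 4% R132H frequency in primary glioblastoma, no positives in the negative tissues, and error-free results outside the failing subtype. They show what the planned outputs could conceal, not what the kit does. This is an inexpensive improvement to the analysis. It does not show that the trial's success rule gives a wrong answer.

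**What to change.** In sections 3.1 and 5, replace the subtype count as a performance measure with the kit-versus-Sanger 2x2 table for each Table 1 subtype, and separately for other brain tumours and normal tissue. Give positive and negative percent agreement with 95% confidence intervals. Group samples by the recorded pathological diagnosis; the HE stain in section 3.2.2 is described as marking tumour area, so it should not be relied on for subtype. Show kit failures with a valid Sanger result as their own row and count them as disagreement, in line with section 4.3(3). Keep R132H frequency as description only, by kit and by Sanger side by side.

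The cost is wording in two sections and one table. No new testing is needed. The drawback is imprecision. An observed 95% agreement has a Wilson interval of 88.8% to 97.8% with 100 relevant samples and 91.0% to 97.3% with 200 (assumed counts), and subtypes with few positives will be much wider. If a firm statement is wanted for a particular subtype, a minimum number of Sanger positives in it should be set in advance.
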